### **15.2. Publications by Investigators**

Pfizer supports the exercise of academic freedom and has no objection to publication by the principal investigator (PI) of the results of the study based on information collected or generated by the PI, whether or not the results are favorable to the Pfizer product. However, to ensure against inadvertent disclosure of confidential information or unprotected inventions, the investigator will provide Pfizer an opportunity to review any proposed

publication or other type of disclosure of the results of the study (collectively, “publication”) before it is submitted or otherwise disclosed.

The investigator will provide any publication to Pfizer at least 30 days before it is submitted for publication or otherwise disclosed. If any patent action is required to protect intellectual property rights, the investigator agrees to delay the disclosure for a period not to exceed an additional 60 days.

The investigator will, on request, remove any previously undisclosed confidential information before disclosure, except for any study- or Pfizer product-related information necessary to the appropriate scientific presentation or understanding of the study results.

If the study is part of a multicenter study, the investigator agrees that the first publication is to be a joint publication covering all investigator sites, and that any subsequent publications by the PI will reference that primary publication. However, if a joint manuscript has not been submitted for publication within 12 months of completion or termination of the study at all participating sites, the investigator is free to publish separately, subject to the other requirements of this section.

For all publications relating to the study, the institution will comply with recognized ethical standards concerning publications and authorship, including Section II - “Ethical Considerations in the Conduct and Reporting of Research” of the Uniform Requirements for Manuscripts Submitted to Biomedical Journals, <http://www.icmje.org/index.html#authorship>, established by the International Committee of Medical Journal Editors.

Publication of study results is also provided for in the CSA between Pfizer and the institution. In this section entitled Publications by Investigators, the defined terms shall have the meanings given to them in the CSA.

If there is any conflict between the CSA and any attachments to it, the terms of the CSA control. If there is any conflict between this protocol and the CSA, this protocol will control as to any issue regarding treatment of study subjects, and the CSA will control as to all other issues.

## Appendix 1. Abbreviations

The following is a list of abbreviations that may be used in the protocol.

Abbreviation	Term
AE	adverse event
Abs	Absolute
$Ae_{12/24}$	amount of unchanged drug excreted into urine from time 0 to 12 hours or 0-24 hours, respectively
$Ae_{12/24}\%$	percentage of dose excreted unchanged into urine from 0 to 12 hours or 0 to 24 hours, respectively
ALP	alkaline phosphatase
ALT	alanine aminotransferase
ANOVA	analysis of variance
AST	aspartate aminotransferase
ATP	adenosine triphosphate
AUC	area under the curve
$AUC_{0-24}$	area under the concentration time curve from time zero to 24 hours after single dose
$AUC_{24}$	area under the concentration-time curve from time 0 to 24 hours
$AUC_{inf}$	area under the concentration-time curve from time 0 to infinity
$AUC_{last}$	area under the concentration-time curve from time 0 to the time of the last quantifiable concentration
$AUC_{tau}$	area under the concentration-time curve over the the dosing interval tau
BA	Bioavailability
BBS	Biospecimen Banking System
BCG	bacille Calmette-Guérin
BE	Bioequivalence
BID	Bis in die (twice a day)
BMI	body mass index
BP	blood pressure
BPM	beats per minute
CCI	
BU	business unit
BUN	blood urea nitrogen
$C_{av}$	average concentration
C-CASA	Columbia-Classification Algorithm of Suicide Assessment
CD	Crohn's disease
CDS	core data sheet

Abbreviation	Term
C eff	efficacious concentration
CFR	Code of Federal Regulations
CHO	Chinese hamster ovary
CI	confidence interval
CK	creatin kinase
CKD	Chronic Kidney Disease
CKD-EPI	Chronic Kidney Disease Epidemiology Collaboration
CL	plasma clearance
CL/F	Apparent total clearance of the drug from plasma after oral administration
CL r	renal clearance
C max	peak or maximum observed concentration
C min	Minimum plasma drug concentration
CCI	
CO 2	carbon dioxide (bicarbonate)
CRF	case report form
CRP	C-reactive protein
CRU	Clinical Research Unit
CSA	clinical study agreement
CSF	cerebrospinal fluid
CSR	clinical study report
CCI	
CT	clinical trial
CTA	clinical trial application
CTC	Common Terminology Criteria
DAI	dosage and administration instructions
DCT	data collection tool
DDI	Drug-drug interaction
DILI	drug-induced liver injury
CCI	
DMC	data monitoring committee
DNA	deoxyribonucleic acid
CCI	
EC	ethics committee
ECG	Electrocardiogram
EDMC	external data monitoring committee
EDP	exposure during pregnancy
EDR	Extemporaneous Dispensing Record

Abbreviation	Term
EDTA	edetic acid (ethylenediaminetetraacetic acid)
eGFR	estimated glomerular filtration rate
EOT	end of treatment
EPO	erythropoietin
ET	early termination
EU	European Union
EIU	exposure in utero
ESoE	Early signal of efficacy
ERB	external review board
EudraCT	European Clinical Trials Database
CCI	
FDA	Food and Drug Administration (United States)
FDAAA	Food and Drug Administration Amendments Act (United States)
FFPE	formalin-fixed paraffin-embedded
FIH	first in human
FISH	Fluorescence in situ hybridization
FSH	follicle-stimulating hormone
GCP	Good Clinical Practice
GFR	glomerular filtration rate
GGT	gamma-glutamyl transferase
GLDH	glutamate dehydrogenase
GLP	Good laboratory practice
GM-CSF	Granulocyte-Macrophage Colony Stimulating Factor
GBP1	Guanylate binding protein 1
HBcAb	Hepatitis B core antibody
HBsAb	Hepatitis B surface antibody
HBsAg	Hepatitis B surface antigen
hCG	human chorionic gonadotropin
HCT	Hematocrit
HCV	Hepatitis C virus
HCVAb	hepatitis C antibody
HDL-C	high density lipoprotein cholesterol
HED	human equivalent dose
HEP	human hepatocytes
HepBcAb	hepatitis B core antibody
HepBsAg	hepatitis B surface antigen
hERG	human ether a-go-go gene
HGB	hemoglobin

Abbreviation	Term
HIV	human immunodeficiency virus
HLM	human liver microsomes
CCI	
HSV	herpes simplex virus
CCI	
HVs	healthy volunteers
HWB	Human whole blood
IB	investigator's brochure
ICH	International Conference on Harmonisation
IC50	50% inhibitory concentration
ID	Identification
IEC	independent ethics committee
IFN	type I interferon
CCI	
IGRA	interferon gamma release assay
IND	investigational new drug application
INR	international normalized ratio
IL	interleukin
IOBU-SDMC	Internal Oncology Business Unit -Safety Data Monitoring Committee
IP	Investigational product
IR	Immediate release
IRB	institutional review board
IRC	internal review committee
CCI	
IUD	intrauterine device
IUS	Intrauterine system
IV	intravenous
JAK	Janus kinase
KDIGO	Kidney Disease: Improving Global Outcomes
KDR	kinase insert domain receptor
K 2 EDTA	dipotassium ethylene diamine tetraacetic acid
LDLC	low density lipoprotein cholesterol
LFT	liver function test
LLN	lower limit of normal
L-PASI	Linear method Psoriasis Area and Severity Index
LPD	local product document

Abbreviation	Term
LSLV	last subject last visit
MAD	multiple ascending dose
MATE	multidrug and toxin extrusion protein
MCH	Mean corpuscular hemoglobin
MCHC	Mean corpuscular hemoglobin concentration
MCV	Mean corpuscular volume
MDR1	multidrug resistant protein 1
MedDRA	medical Dictionary for Regulatory Activities
mRNA	messenger riboneuclic acid
MTD	maximum tolerated dose
MRP	multidrug resistance-associated protein
MRT	mean residence time
NAPAC	Neuropsychiatric and Abuse Potential Advisory Council
N/A	not applicable
NK	Natural Killer cell
CCI	
NOAEL	no observed adverse effect level
NOEL	no observed effect level
NRS	Numeric Rating Scale
NTCP	sodium/taurocholate co-transporting polypeptide
OATP	organic anion transporting polypeptide
OBU	Oncology Business Unit
OCT	organic cation transporter
OEB5	occupational exposure banding 5
CCI	
PBMC	peripherhal blood mononucleated cell
PCD	primary completion date
PCRU	Pfizer Clinical Research Unit
PD	Pharmacodynamics
PGx	Pharmacogenomics
P-gp	P glycoprotein
PHQ-8	Patient health questionnaire
PI	principal investigator
PK	Pharmacokinetics
PR	pulse rate
PROs	patient reported outcomes
PT	prothrombin time
CCI	
PUVA	Psoralen ultraviolet A
QC	quality control
QD	Once daily
QFT	QuantiFERONR TB
QFT-G	QuantiFERONR TB Gold

Abbreviation	Term
QFT-GIT	QuantiFERON TB Gold In Tube test
QTc	corrected QT
RBC	red blood cell
RNA	ribonucleic acid
RSAD2	radical S-adenosyl methionine domain-containing protein 2
S Cystatin C	serum Cystatin C
SAD	ascending dose period
SAE	serious adverse event
SAP	statistical analysis plan
SBQ-R	Suicidal behaviors questionnaire
SCr	serum creatinine
sd	single dose
SDD	sprayed-dried dispersion
SGOT	serum glutamic oxaloacetic transminase
SGPT	serum glutamic pyruvic transminase
SIB	suicidal ideation and behavior
SLE	Systemic lupus erythematosus
SOP	standard operating procedure
SRSD	single reference study document
ss	steady state
STAT	Signal Transducer and Activator of Transcription
T 1/2	terminal half life
Tau	dosing interval of 12 or 24 hours
TB	tuberculosis
TBili	total bilirubin
TC	Total cholesterol
TG	Total triglycerides
Th1	T-helper 1
Th17	T-helper 17
Tmax	time to reach maximum concentration
THC	Tetrahydrocannabinol
CCI	
CCI	
UGT	UDP-glucuronosyltransferase
ULN	upper limit of normal
US	United States
USP18	ubiquitin specific peptidase 18
USPI	United States package insert
UV	ultraviolet
UVA	ultraviolet A
UVB	ultraviolet B
VEGFR2	vascular endothelial growth factor receptor 2
Vss	Apparent volume of distribution at steady state

Abbreviation	Term
V z /F	apparent oral volume of distribution
CCI	[REDACTED]
WBC	white blood cell

## **Appendix 2. Cockcroft-Gault Calculation**

The Cockcroft-Gault formula may be used to calculate an Estimated Creatinine Clearance, which in turn estimates Glomerular filtration rate (GFR)

$$\text{Est. Creatinine Clearance (mL/min)} = \frac{([140 - \text{Age}(\text{years})] \times \text{Weight}(\text{kg}) \times \text{Factor}^{\text{a}})}{(72 \times \text{Serum Creatinine [mg/dL]})}$$

a Factor is equal to 0.85 in females, and 1.00 in males

### Appendix 3. Prohibited Concomitant Medications

#### CYP1A2, CYP3A4, CYP2D6

##### **Inhibitors**

*CYP 1A2*  
Ciprofloxacin  
Clinafloxacin  
Enoxacin  
Fluvoxamine  
Oltipraz  
Rofecoxib  
Zafirlukast

Etintidine  
Idrocilamide  
Methoxsalen  
Mexiletine  
Oral contraceptive  
Phenylpropanolamine  
Pipemidic acid  
Propafenone  
Propranolol  
Troleandomycin  
Vemurafenib

*CYP 2D6*  
Quinidine  
Fluoxetine  
Dacomitinib  
Paroxetine  
Bupropion

Cinacalcet  
Terbinafine  
Tipranavir  
Moclobemide  
Rolapitant  
Mirabegron  
Duloxetine  
Eliglustat  
Dronedarone

*CYP3A4*  
Viekira pak  
Indinavir  
Tipranavir

#### CYP1A2, CYP3A4,

##### **Inducers**

*CYP 1A2*  
Phenytoin  
Rifampin  
Ritonavir  
Teriflunomide

*CYP3A4*  
Rifampin  
Mitotane  
Avasimibe

#### MATE substrates

Dofetilide  
Metformin

**CYP1A2, CYP3A4, CYP2D6**

**Inhibitors**

Ritonavir  
Cobicistat  
  
Ketoconazole  
Troleandomycin  
Telaprevir  
Danoprevir  
Elvitegravir  
Saquinavir  
Lopinavir  
Itraconazole  
Voriconazole  
Mibefradil  
Clarithromycin  
Posaconazole  
Telithromycin  
Grapefruit Juice  
Conivaptan  
Nefazodone  
Nelfinavir  
Saquinavir  
Idelalisib  
Boceprevir  
  
Erythromycin  
Fluconazole  
Atazanavir  
Darunavir  
Diltiazem  
Dronedarone  
Crizotinib  
Aprepitant  
Casopitant  
Amprenavir  
Faldaprevir  
Imatinib  
Verapamil  
Netupitant  
Nilotinib  
Tofisopam  
Cyclosporine  
Ciprofloxacin  
Isavuconazole  
Cimetidine

**CYP1A2, CYP3A4,**

**Inducers**

Phenytoin  
Carbamazepine  
  
Enzalutamide  
St. John's wort  
Rifabutin  
Phenobarbital  
  
Semagacestat  
Efavirenz  
Bosentan  
Genistein  
Thioridazine  
Nafcillin  
Talviraline  
Lopinavir  
Modafanil  
Etravirine  
Lersivirine

**MATE substrates**

#### Appendix 4. Estimated Glomerular Filtration Rate

The estimated GFR (eGFR) will be calculated using the 2 sets of equations developed by the Chronic Kidney Disease Epidemiology Collaboration (CKD-EPI), which utilize serum creatinine (SCr) and serum Cystatin C (S Cystatin C) respectively.

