#### 7.1.11. Serum Creatinine and Serum Cystatin-C

Serum creatinine is the best known standard test for monitoring renal function. However, serum creatinine based estimates of glomerular filtration rate (eGFR) may be affected by factors other than renal function, including chronic and acute illness. Cystatin C is a test that can be used either as an adjunct to or a replacement for serum creatinine. The most reliable estimates of GFR use both test results.

Cystatin C is a low molecular weight protein that is used as an alternative to serum creatinine for monitoring of renal function. It seems to correlate more closely with GFR than does serum creatinine concentration and may be a more sensitive detector of early renal dysfunction. While use of cystatin C has been limited, its independence of demographic

factors (eg, race) has made it an interesting means of determining changes in renal function in clinical settings and it is included in the 2012 Kidney Disease: Improving Global Outcomes (KDIGO) guidelines. Estimated GFR may be calculated via the 2012 Chronic Kidney Disease Epidemiology Collaboration equation (CKD-EPI) creatinine, cystatin C, or creatinine-Cystatin C equations.

Serum creatinine and serum cystatin C will be measured from the serum chemistry specified in the [Schedule of Activities](#) section of the protocol. Serum creatinine and cystatin C based eGFR will be calculated at baseline and end of treatment (EOT) at a minimum (additional time points may be assessed).

When a subject has an increase in serum creatinine of  $\geq 0.3$  mg/dL relative to the subject's baseline, and after that increase has been confirmed by a (single) repeat test obtained as soon as practically feasible, but within 24 hours of the initial result, this will trigger assessment of serum cystatin-C in order to facilitate both cystatin C based and serum creatinine based eGFR calculations.

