#### **7.1.12. Estimated Glomerular Filtration Rate**

Serum creatinine and serum cystatin-C based estimated GFR (eGFR) will be calculated at baseline and end of study treatment period at a minimum for all subjects, in order to facilitate calculation of eGFR at these time points. When cystatin-C testing is performed during the treatment period, corresponding serum creatinine and cystatin-C based eGFR will be determined to support assessment of renal function.

The respective estimated GFR (eGFR) values will be calculated using the 2 sets of equations developed by the Chronic Kidney Disease Epidemiology Collaboration (CKD-EPI), which utilize serum creatinine (SCr) and serum Cystatin C (S Cystatin C) respectively. ([Appendix 4](#)).

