## **7.12. Triggered Requirements**

### **7.12.1. Potential Cases of Acute Kidney Injury**

Abnormal values in serum creatinine (SCr) concurrent with decline in eGFR that meet the criteria described below in the absence of other causes of kidney injury, are considered potential cases of acute kidney injury and should be considered important medical events. An increase of  $\geq 0.3$  mg/dL (or  $\geq 26.5$   $\mu\text{mol/L}$ ) in serum creatinine relative to subjects' own baseline measurement should trigger another assessment of SCr to confirm, within 24-hours from awareness.

If the second (repeat) result is still of  $\geq 0.3$  mg/dL (or  $\geq 26.5$   $\mu\text{mol/L}$ ) relative to subject baseline, assessment of serum Cystatin C (S Cystatin C) should be referenced. Based on these measurements, estimated GFR using serum creatinine (2009 CKD-EPI eGFR^7) and serum cystatin C (2012 CKD-EPI eGFR^7) will be determined and reviewed, preferably within 72 hours and not later than 96 hours from the confirmed (repeat) elevated serum creatinine result.

If an individual subject demonstrates CONCOMITANT sCr-based AND S Cystatin C-based eGFR decline of  $\geq 30\%$  compared to the subject's baseline eGFR, then the subject should not be further dosed and adequate, immediate, supportive measures including **immediate evaluation by a nephrologist (preferably within 24 hours) with appropriate management** and treatment as clinically indicated. Results should be repeated as indicated by the nephrologist or weekly at a minimum until the eGFR returns to baseline  $\pm 15\%$  or the renal parameters are deemed to be stable by the nephrologist and/or PI.

**If the subject cannot be seen by a nephrologist within 24 hours (as described above), then the subject should be sent to a local emergency room for evaluation and treatment as clinically indicated.**

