##### CKD-EPI2009Scr

If female and SCr is  $\leq 0.7$  mg/dL:

- $GFR (mL/min/1.73 m^2) = 144 \times (Scr/0.7)^{-0.329} \times 0.993^{age} (x 1.159, \text{ if black})$

If female and SCr is  $> 0.7$  mg/dL:

- $GFR (mL/min/1.73 m^2) = 144 \times (Scr/0.7)^{-1.209} \times 0.993^{age} (x 1.159, \text{ if black})$

If male and SCr is  $\leq 0.9$  mg/dL:

- $GFR (mL/min/1.73 m^2) = 141 \times (Scr/0.9)^{-0.411} \times 0.993^{age} (x 1.159, \text{ if black})$

If male and SCr is  $> 0.9$  mg/dL:

- $GFR (mL/min/1.73 m^2) = 141 \times (Scr/0.9)^{-1.209} \times 0.993^{age} (x 1.159, \text{ if black})$

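### In women with baseline creatinine of about 0.60 to 0.87 mg/dL the 0.3 mg/dL trigger comes after a 30% fall in creatinine-based eGFR, and the protocol conflicts on whether cystatin C and eGFR are routine

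*Protocol*

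**What the plan says.** Appendix 4 sets out the equations: "The estimated GFR (eGFR) will be calculated using the 2 sets of equations developed by the Chronic Kidney Disease Epidemiology Collaboration (CKD-EPI". One set uses creatinine and the other cystatin C. The creatinine set has separate forms for each sex, with a change of slope at 0.7 mg/dL in women and 0.9 mg/dL in men.

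Section 7.12.1 works in sequence. A creatinine rise of at least 0.3 mg/dL "relative to subjects' own baseline measurement should trigger another assessment of SCr to confirm, within 24-hours from awareness". If the repeat agrees, cystatin C is consulted and both eGFRs are reviewed. The action step follows: "If an individual subject demonstrates CONCOMITANT sCr-based AND S Cystatin C-based eGFR decline of" at least 30% from baseline, that subject is not dosed again. The section also has a cohort count. If two or more healthy subjects in a cohort each show two successive falls of at least 30% on both markers, the finding is assessed as a possible drug reaction.

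Three other places bear on when eGFR is available:

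- Table 7 lists serum cystatin C in the chemistry panel.
- Section 7.1.11 says creatinine and cystatin C both come from the scheduled chemistry sample. It then sets a floor, "Serum creatinine and cystatin C based eGFR will be calculated at baseline and end of treatment (EOT) at a minimum", with further time points optional. Its last paragraph makes a confirmed 0.3 mg/dL rise the event that prompts cystatin C.
- Section 7.1.12 says: "When cystatin-C testing is performed during the treatment period, corresponding serum creatinine and cystatin-C based eGFR will be determined". It sets no condition on the size of any creatinine rise.

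**The concern.** An entry trigger should be reached no later than the criterion it leads to. Otherwise a subject can meet the criterion, or half of it, before anyone is told to look. The trigger here is an absolute rise and the criterion is a relative fall through a two-slope equation, so their order depends on sex and baseline creatinine. For one group of women the order reverses.

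That would matter little if both eGFRs were calculated at every chemistry draw anyway. The protocol does not settle this: some passages make cystatin C and eGFR routine, and others make them conditional. At stake is a subject-level rule on continued dosing and a cohort-level signal. The protocol itself singles out renal function for extra monitoring, because the drug may inhibit renal transport of creatinine (section 1.3.1).

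**Working it through.** **Inputs.** From Appendix 4: in women the knot k is 0.7 mg/dL, with exponent a = -0.329 at or below it; in men k = 0.9 and a = -0.411; above the knot the exponent is -1.209 in both. From 7.12.1: trigger, a rise of at least 0.3 mg/dL; criterion, a fall of at least 30%. The documents state no figure linking the two, so there is none to reproduce.

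**Formula.** Let g(s) = (s/k)^a for s at or below k, and (s/k)^-1.209 above it. For baseline b and rise r, the decline is 1 - g(b+r)/g(b). The leading constant, age and race factors cancel within a subject.

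**Women, baseline at or above 0.70.** A 30% decline needs (b+r)/b = 0.70^(-1/1.209) = 1.34315, so r = 0.34315b. This is below 0.30 when b is below 0.30/0.34315 = 0.874.

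**Women, baseline below 0.70.** Example b = 0.65: g(b) = (0.65/0.7)^-0.329 = 1.0247. The target is 0.70 x 1.0247 = 0.7173, so b+r = 0.7 x 0.7173^(-1/1.209) = 0.921 and r = 0.271. Solved numerically, the lower edge of the band is b = 0.603.

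| Baseline, women (mg/dL) | Rise giving a 30% decline | Decline at a rise of 0.30 |
|---|---|---|
| 0.60 | 0.302 | 29.9% |
| 0.65 | 0.271 | 32.5% |
| 0.70 | 0.240 | 35.0% |
| 0.75 | 0.257 | 33.4% |
| 0.80 | 0.275 | 32.0% |
| 0.85 | 0.292 | 30.6% |
| 0.88 | 0.302 | 29.9% |

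**Men.** The smallest rise giving a 30% decline is 0.34315 x 0.90 = 0.309, at baseline 0.90. The largest decline at a rise of 0.30 is 29.4%, at the same baseline. The trigger always comes first.

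**Reporting precision (assumption; the documents give none).** At 0.01 mg/dL the gap covers baselines 0.62 to 0.84 and rises 0.25 to 0.29. For example, 0.70 to 0.95 gives 1 - (0.95/0.70)^-1.209 = 30.9%. At 0.1 mg/dL the largest rise below the trigger is 0.2, and the worst case, 0.7 to 0.9, gives 1 - (0.9/0.7)^-1.209 = 26.2%. No gap remains.

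**The other creatinine stopping rule.** Sections 3.3 and 3.4 stop dosing at 1.5 x ULN. Entry requires screening creatinine at or below ULN (4.2, 4.4). If her baseline is also at or below ULN, then 1.5 x ULN is at least 1.5b, which exceeds b + 0.3 whenever b is above 0.6. That is the whole band, so this rule does not fill the gap.

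**Can such women enrol?** Entry needs a Cockcroft-Gault value above 80 mL/min. A woman aged 55 weighing 65 kg passes with creatinine below (140-55) x 65 x 0.85/(72 x 80) = 0.815 mg/dL. The band is reachable.

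**The cystatin half.** From a baseline at or above 0.8 mg/L, a 30% fall needs cystatin C to rise by a factor of 0.70^(-1/1.328) = 1.308. Below 0.8 the relative rise must be larger. The creatinine arithmetic does not show that this occurs.

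**Is eGFR routine?**

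- Routine: Table 7, the sample-source sentence of 7.1.11, and 7.1.12 together give both eGFRs at each chemistry draw. Tables 9 and 10 count 7 treatment-period safety-laboratory draws in MAD and 9 in the psoriasis cohorts.
- Conditional: the 7.1.11 floor of baseline and end of treatment, plus its closing paragraph. On the floor alone there is one post-baseline eGFR, which cannot supply the two successive falls in the 7.12.1 cohort count.

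**The case against.** The strongest reply is that the protocol already provides the safeguard. Cystatin C is on the chemistry panel, it is measured from scheduled samples, and 7.1.12 requires both eGFRs whenever it is tested on treatment. The wording in 7.12.1 about consulting cystatin C fits a value already on file. This stands as one available reading, and it defeats the stronger claim a reader might infer, that a qualifying decline will go unassessed during dosing. It does not remove the conflict. If every draw yielded both eGFRs, the closing paragraph of 7.1.11 and the two-time-point floor would serve no purpose. Nor does 7.1.12 say that a routinely derived eGFR feeds the 7.12.1 action step without the creatinine step.

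A second reply is that the 0.3 mg/dL rise belongs to the case definition, since 7.12.1 opens by pairing abnormal creatinine with an eGFR fall. A smaller rise would then be outside the definition and not a missed case. But later in 7.12.1 confirmed cases are identified by the eGFR test, which makes the rise look like an entry step.

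Other points stand as limits. Both markers must fall, and only the creatinine side is shown here. Inhibited creatinine transport would raise creatinine without a true fall in filtration, so the trigger would fire more readily while cystatin C stayed put. Only women of non-childbearing potential are eligible. SAD is a single dose. MAD dosing lasts 10 days, with eGFR at the end of treatment and 24-hour creatinine clearance on Day -1 and Day 10. The cohort count names no creatinine trigger, so the documents do not establish that it would miss these same women.

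**Conclusion.** The concern holds in limited form. Under the protocol's own equation, the trigger does not cover the creatinine half of the 30% criterion in women with baseline creatinine of 0.603 to 0.874 mg/dL. Declines from 30% to just under 35.0% can sit below it. Men are unaffected. This assumes creatinine reported finely enough: at 0.01 mg/dL the affected baselines are 0.62 to 0.84, and at 0.1 mg/dL there are none.

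A reader might infer that women who meet the full criterion will be left on drug unrecognised. The documents do not support that. It requires a concurrent cystatin-based fall of at least 30%, and it requires cystatin C to be treated as a triggered test, which is only one of two readings. The number of women affected cannot be estimated from the documents.

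What is established is a mismatch between trigger and criterion in one sex, together with conflicting text on whether the values that would reveal it are produced during dosing. Because this is a safety rule and the correction is cheap, the sponsor should act.

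**What to change.** First, reconcile 7.1.11, 7.1.12, Table 7 and 7.12.1 on whether cystatin C and both eGFRs are routine during treatment. If cystatin C is on the panel as Table 7 states, derive both Appendix 4 eGFRs at each scheduled chemistry draw. Bring the closing paragraph of 7.1.11 and its time-point floor into line, and say which eGFR values feed the cohort count. State the reporting precision of creatinine.

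Second, the sponsor should reconcile the 0.3 mg/dL trigger with the 30% criterion and state whether the criterion applies when the trigger has not been met. That is a clinical decision; no threshold or stopping rule is proposed here.

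The cost is protocol wording and a derived laboratory variable at existing draws. No new samples are needed if cystatin C is already run on the panel. The downside is a few more values to review.
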